The trial design is simple in structure, and aims to compare the effects of MBT-PP against TAU on a range of measures. Participants (parents and children) will complete baseline measures before being randomised to receive either MBT-PP or TAU. After 16 weeks (when MBT-PP is complete) the baseline measures will be repeated (post-intervention). Three months after the end of the intervention (3-month follow-up), measures will be repeated a final time. The inclusion of a number of secondary measures enables the trial not only to answer the question of whether MBT-PP is effective in improving child outcomes as measured by the SDQ, but also to identify the mechanisms of action for these positive effects.

A concurrent implementation and process evaluation (IPE) will run throughout both the pilot and efficacy phases. The IPE will be designed to generate insights into the challenges associated with formulating the referral pathways, as well as the processes associated with the delivery of the intervention.

Intervention

MBT-PP

Tavistock Relationships' Mentalization Based Therapy – Parenting Under Pressure (MBT-PP) is a 10-week intervention for parents which is suitable for separated parents or intact couples. The 10 sessions across 16 weeks include 2 assessment sessions and 8 sessions that begin by introducing the skills and behaviours necessary for mentalizing: the capacity to hold others in mind when emotionally aroused and to avoid a swift eruption of conflict. The subsequent sessions build on this ability to think about parents' own feelings and beliefs, those of their partner, and the needs of their children, ending with a focus on how to maintain the achievements made.

Who: The target population for this intervention is parents of children experiencing high levels of persistent and unresolved conflict. The intervention is delivered to parents only – there is no direct therapeutic work with children. This evaluation focuses specifically on parents of children aged 8-14 years. Recruitment will be via referrals from Early Help in 3 local authorities: Dorset Council, Bournemouth, Christchurch, and Poole (BCP) Council, and Bristol City Council.

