What: The intervention consists of MBT-PP, delivered online. After an initial assessment period, which consists of individual sessions for each parent with the therapist, both parents will take part in joint sessions, online, with the therapist. If only one parent is willing to take part, the therapist will work with that parent on their own. MBT-PP is delivered by MBT-PP practitioners, all of whom are qualified therapists, counsellors, family therapists, or child and adult psychotherapists, accredited and registered with their relevant professional bodies (BACP, UKCP, AFT etc.) and compliant with the requirements of these professional bodies, including ethical standards and professional supervision. Treatment fidelity is supported through fortnightly group supervision, offered by MBT-PP Supervisors who have received additional training. Supervisors attempt to ensure adherence to, and prevent departure from the manualised intervention. This allows TR to maintain fidelity, clinical oversight, manage risk and develop practitioners' skills further. Supervisors' work, in turn, is overseen by monthly supervision of supervisors, delivered by the most experienced MBT-PP leaders.

How much: The intervention consists of 10 sessions delivered over (approximately) 16 weeks. The first 2 sessions last up to 75 minutes, and sessions 3-7 inclusive last 60 minutes. Sessions are usually delivered weekly or fortnightly, allowing participants some scheduling flexibility. Sessions are delivered online, via secure Zoom or Teams calls, depending on client preference.

Treatment as usual (TAU)

Because of the aforementioned under-developed pathways for tackling IPC in LAs, it is likely that true TAU, that is, what would occur in the absence of this trial, will vary extremely widely. Because of the nature of family support provision by LAs, understanding the precise nature and content of all the possible interventions is not possible. For example, we would not be able to appraise the intensity or content of family support worker visits to a family home, in which the impact of IPC on the children may either become a focal point, or be tackled much more indirectly, if at all. In this scenario it would be very difficult to understand whether the active ingredients of MBT-PP are in fact unique to the intervention received in the MBT-PP arm.

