Secondary analyses will address the secondary questions of whether, compared to TAU, MBT-PP produces: reduced IPC, lower child perception of IPC, improved parenting style, reduced parent anger expression, improved parent emotional adaptation to the situation, and improved CYP psychological well-being.

Mediation analyses using structural equation modelling will be employed to test whether IPC, lower child perception of IPC, reduced parent anger expression, and improved parent emotional adaptation to the situation are significant mechanisms by which MBT-PP improves CYP adjustment (parent report SDQ scores).

Descriptive statistics will be used to compare the demographics of the sample to the local populations of the LAs. Dropout analyses will be used to assess whether there were systematic differences between participants who were and were not compliant with MBT-PP.

Quantitative data will initially be analysed to establish the extent and nature of any missing data (i.e. MCAR, MCR MNAR). An appropriate imputation solution will be implemented and the ITT analyses will be re-done using this imputed data as sensitivity analyses.

Any parametric test assumptions will then be evaluated and violations to assumptions will be addressed as appropriate (e.g. through data transformations).

Data will be aggregated across the pilot and efficacy studies either pooling the data or using meta-analytic techniques, depending on any design changes that occur from pilot to efficacy, to produce the overall impact estimates of the efficacy study with internal pilot.

All planned statistical analyses will be set out in the Statistical Analysis Plan (SAP) prior to any analysis taking place.

Longitudinal follow-ups

It is possible that the effects of MBT-PP are not seen immediately that the therapy finishes, but take some time to embed into the family system in a way that effects change. We therefore plan to conduct a 3-month follow up. This will take place 3 months from the last session of MBT-PP, or, for those in TAU, 7 months (the length of MBT-PP + 3 months) after the baseline measures. All baseline measures will be repeated.

The analytic procedures employed to analyse the follow up data will be the same as those used to analyse the post-intervention data (but with an additional time point). All analyses will be fully specified in the SAP.

Implementation and process evaluation

Implementation Research Questions (RQs)

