This trial is running in 3 local authorities, Bristol, Dorset, and Bournemouth, Christchurch, and Poole (BCP). In each local authority, this evaluation funds a 'Gateway Lead' post. Postholders are staff with experience of working with CYP and families and have backgrounds in primary teaching and family support.

Gateway Leads have created referral pathways into the project and promoted awareness of the project in schools and other relevant local authority staff. When referred, families are screened for eligibility against exclusion and inclusion criteria and taken through the consent

process. Once consent is obtained, families complete baseline assessments, and are subsequently randomly allocated to receive either MBT-PP or TAU. Allocation is conducted by the evaluator according to a minimisation protocol to ensure a balanced sample. Families then undergo their allocated treatment. Once treatment has completed, families complete post-intervention assessments. Follow up assessments are completed 3 months later.

The primary outcome variable for this trial is the ‘Total Difficulties’ (TD) subscale of the Strengths and Difficulties Questionnaire (SDQ; Goodman, 1997) obtained from the mothers’ post-intervention assessment, reporting on the CYP. As such, analyses will focus on comparing mothers’ post-intervention TD scores between MBT-PP and TAU. Secondary outcome variables are fathers’ post-intervention TD score; and child psychological well-being (as measured by the Stirling Children’s Well-being Scale, Liddle & Carter, 2015).

The trial is also assessing proposed mechanisms of action, by assessing: parent report IPC (as measured by the O’Leary-Porter Scale, OPS, Porter & O’Leary, 1980, adapted as described in the protocol); child perception of IPC (as measured by the Perceptions of Interparental Conflict-Intensity/Frequency Scale, PIC-I/F, Kline, Wood & Moore, 2003); parent anger (as measured by the Dimensions of Anger Reactions-Revised, DAR-R, Nederlof et al., 2009); parent mentalising capacity (as measured by the Parental Reflective Function Questionnaire, PRFQ, Luyten et al., 2009); parenting style (as measured by the Parenting Scale Short Form, PS-8, Kliem et al., 2019); and, for separated parents only, parent emotional adaptation to separation (as measured by the Emotional Adaptation to Relationship Dissolution Assessment, EARDA, Millings et al., 2020).

Table 1. Trial design overview

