- $\beta_{4..7}$ are the coefficient estimates for the four family-level dummy variables.

² This because centring the CYP level scores around their cluster (family) mean is an orthogonal transformation, CYP scores are placed relative to their family mean and so will not share any variance ($r = 0$).

- ϑ'_j and ε'_{ij} are random effects that remain at the school and pupil levels and are assumed to be distributed normally in the population with zero means, variances σ_c^2 and τ_c^2 respectively, and for these variances to be conditionally uncorrelated.

The estimate of impact will be standardised as an effect size by dividing by the standard deviation obtained from the variance partition estimates for the empty/null model described in equation 2.1:

$$[2.1] \quad Y_{ij} = \beta_0 + \vartheta_j + \varepsilon_{ij}$$

Where:

- β_0 is the constant term for the empty model and represent the mean mothers reported SDQ-TD for CYP at T2 (16 weeks following minimisation).
- ϑ_j and ε_{ij} are random effects at the school and pupil levels and are assumed to be distributed normally in the population with zero means, variances σ^2 and τ^2 respectively.

Table 5 summarises the ITT analysis for the mothers SDQ-TD primary outcome described in equation 2.0.

Table 5. Example analysis model for mothers SDQ-TD primary outcome (RQ1a)

Analysis and Sample	Level 1 (CYP) Covariates	Level 2 (Family) Covariates	Outcome Variable
Null/Empty model			CYP level mothers SDQ-TD (raw) score at T2 (16 weeks following minimisation)
Final Model	Mothers SDQ-TD score at T1/baseline (Centred around family mean)	Mean mothers SDQ-TD score at T1/baseline (Centred around grand mean) Group membership (MBT or TAU) Four Minimisation Dummy Variables: CYP ages (2); parental ethnicity (1), relationship status (1);	CYP level mothers SDQ-TD (raw) score at T2 (16 weeks following minimisation)

The empty model is described by equation 2.1 and the final model by equation 2.0. The impact of the MBT-PP programme (compared with TAU) amongst parents experiencing IPC on

mothers SDQ-TD scores will be estimated using the coefficient for the group membership family-level covariate included in the final model (β_1 in equation 2.0). Impact will be standardised into an effect size by dividing the β_1 coefficient shown by the unconditional standard deviation from the null/empty model described in equation 6.0 below.

Secondary outcome analysis

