To examine the influence of time we will first statistically summarise the time (in weeks⁵) between baseline (T1) and outcome (T2) and the bivariate relationship between time and the mothers SDQ TD outcome at T2 for the MBT and TAU groups. Following this we will take a similar approach to the CYP age subsample analysis and introduce time (in weeks) as a CYP-level main effects term (centred around the CYP level mean; CYP_CWeeks_{ij}) and as an interaction with the family-level group identifier ($T_j \times CYP_CWeeks_{ij}$) in a hierarchical linear model, as described in equation 5.0:

$$[5.0] Y_{ij} = \beta_0 + \beta_1 T_j + \beta_2 (X_{ij} - \bar{X}_j) + \beta_3 (\bar{X}_j - \bar{X}) + \beta_4 CYP_CWeeks_{ij} + \beta_5 T_j \times CYP_CWeeks_{ij} + \beta_{6..9} [MIN DUM]_j + \vartheta_j + \varepsilon_{ij}$$

If the β_5 main effects term for time is statistically significant, this would indicate that mothers SDQ TD at T2 was associated with the number of weeks between baseline (T1) and outcome (T2) measures. This would not necessarily indicate a problem with the estimate of impact from the ITT analysis but would provide useful context. However, if the β_5 interaction coefficient is observed to be statistically significant, this would raise a question on the validity

⁵ Measured in days but included as decimalised 'weeks' with the assumption of a mean of 16.0 weeks.

of the ITT estimate (because the interaction term would suggest that this estimate depended on the amount of time between T1 and T2). If the β_5 interaction coefficient is observed to be statistically significant, the sign would indicate whether increased time (weeks between T1 and T2) resulted in higher (positive) or lower (negative) estimates of impact. Follow-on analyses would be undertaken on subsamples of participants determined by time. This might be three subsamples (below mean, mean, above mean) but is dependent on subsample size and will be determined following an examination of the data.

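### T3 is counted from the last MBT-PP session in one arm and from baseline in TAU, with no rule for early leavers or never-starters, and the documents disagree on T2 and T3 timing

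*Protocol*

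**What the plan says.** **T3.** The Protocol (Longitudinal follow-ups) sets it by arm: "This will take place 3 months from the last session of MBT-PP, or, for those in TAU, 7 months". The TAU figure in full is "7 months (the length of MBT-PP + 3 months) after the baseline measures". The Protocol's Evaluation Design section instead places T3 three months after the intervention ends, with no separate rule for TAU. The SAP (Design overview) counts it from the post-intervention assessment: "Once treatment has completed, families complete post-intervention assessments. Follow up assessments are completed 3 months later".

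**T2.** The Protocol (Evaluation Design) equates two things: "After 16 weeks (when MBT-PP is complete) the baseline measures will be repeated (post-intervention"). The SAP model (equation 2.0, Table 5) fixes the outcome at "T2 (16 weeks following minimisation"). The SAP Design overview, quoted above, ties it to the completion of treatment.

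**Pacing.** The Protocol (Intervention, MBT-PP) states "The intervention consists of 10 sessions delivered over (approximately) 16 weeks" and "Sessions are usually delivered weekly or fortnightly, allowing participants some scheduling flexibility".

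**Who is analysed.** The Protocol (Intervention delivery) keeps families found unsuitable at clinical assessment in their allocated arm. The SAP (Analysis) keeps every CYP as allocated, irrespective of take-up.

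**Timing checks.** The SAP (Further analyses) summarises and models the T1 to T2 interval. If the time-by-arm interaction is significant, "Follow-on analyses would be undertaken on subsamples of participants determined by time". No equivalent is written for T3.

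**The concern.** In TAU the T3 clock starts at baseline. In MBT-PP it starts at an event after randomisation whose date depends on how quickly sessions are booked and whether the family stays. Two arms that are comparable at randomisation can then be measured at different elapsed times, for reasons linked to engagement. Children's SDQ scores may change with time whatever the treatment, and any such change would be mixed with the treatment effect.

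Elapsed time is also central to the purpose of T3. The Protocol includes the follow-up because effects may emerge only some time after therapy ends. What is at stake is the 18 T3 outcomes in SAP Table 4, all secondary, and the SEM models that the SAP proposes to repeat with T3 outcomes if enough responses are received.

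The disagreement over T2 is a separate matter that touches the primary time point. TAU is guided use of digital resources with no fixed length, so a T2 rule based on completion of treatment gives no clear date in that arm.

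**Working it through.** **Inputs.** MBT-PP takes ten sessions over about 16 weeks, spaced 1 or 2 weeks apart (Protocol, Intervention). TAU T3 is at 7 months (Protocol, Longitudinal follow-ups). Assumptions: baseline and minimisation fall on the same day, and session 1 falls either on that day or 2 weeks later. The 2-week lag is illustrative, borrowed from the therapist-contact benchmark in Appendix A, criterion 6.

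**Conversion.** 1 month = 365.25 / 12 / 7 = 4.348 weeks, so 3 months = 13.04 weeks.

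**The plan's own figure.** 16 + 13.04 = 29.04 weeks, and 29.04 / 4.348 = 6.68 months, which rounds to 7. The stated 7 months is reproduced. In weeks, 7 × 4.348 = 30.44. The nominal gap is 30.44 − 29.04 = 1.39 weeks before rounding, or 9.75 days.

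**MBT-PP due date.** T3 week = lag + (k − 1) × spacing + 13.04, where k is the last session attended. Values in brackets use the 2-week lag.

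| MBT-PP family | Last session (week) | T3 due (week) | Difference from TAU (weeks) |
|---|---|---|---|
| Takes 16 weeks | 16 | 29.0 | −1.4 |
| All ten, weekly | 9 (11) | 22.0 (24.0) | −8.4 (−6.4) |
| All ten, fortnightly | 18 (20) | 31.0 (33.0) | +0.6 (+2.6) |
| Leaves after session 1 | 0 (2) | 13.0 (15.0) | −17.4 (−15.4) |
| Leaves after session 3, weekly | 2 (4) | 15.0 (17.0) | −15.4 (−13.4) |
| Leaves after session 3, fortnightly | 4 (6) | 17.0 (19.0) | −13.4 (−11.4) |
| Leaves after session 5, weekly | 4 (6) | 17.0 (19.0) | −13.4 (−11.4) |
| Leaves after session 5, fortnightly | 8 (10) | 21.0 (23.0) | −9.4 (−7.4) |

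The rows for leavers apply only if the last session means the last one attended. On that reading, with T2 fixed at 16 weeks, T3 coincides with T2 when the last session falls at week 16 − 13.04 = 2.96. If the phrase means the programme's final session, those rows have no date. A family that attends nothing has no date on either reading.

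**The other wording.** Taking the SAP model (T2 at 16 weeks after minimisation) with the SAP Design overview (T3 three months later) gives 16 + 13.04 = 29.0 weeks for every randomised family in both arms. The Protocol's arm-specific rule matches this only for an MBT-PP family whose last session falls at week 16.

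**T2 rules side by side.** Sixteen weeks from minimisation and completion of treatment agree for a family that finishes at week 16. For ten sessions with no lag they differ: completion falls at week 9 if weekly and week 18 if fortnightly.

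**The case against.** The best defence is that the arms were deliberately matched: 7 months is derived from the length of MBT-PP plus three months, and the nominal difference is about 10 days. Measuring three months after therapy also has a stated rationale. Both points stand. A reader might infer that all 18 T3 outcomes compare the arms at unequal times by design. The documents do not support that. Unequal timing can arise, through pacing or early leaving.

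Three other strong readings also go too far:

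- **Early leavers are due T3 at about T2.** The Protocol does not say the last session attended. Even on that reading, T3 meets T2 only for a last session near week 3 with T2 held at 16 weeks. Leaving after session 5 gives weeks 17 to 23. Under the SAP Design overview, T3 follows T2 by three months, so the two cannot coincide.
- **Never-starters have no T3 date at all.** That is true of the Protocol's rule alone. The SAP wording taken together implies about week 29.
- **A large share of the MBT-PP arm is affected.** The 25% and 50% limits in Appendix A, criterion 3, are progression tolerances for clients with fewer than six sessions. They are not expected rates, and that group is much wider than the families whose T3 would fall near T2.

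The SAP's time analysis is a diagnostic and does not claim to repair the comparison, so removing it would be a matter of preference. Applying the primary analyses to T3, as the SAP plans, arguably carries the time check over, although this is not written. The check would also condition on an interval that is itself affected by attendance.

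None of this supplies the missing rule for non-completers or removes the conflict between the documents.

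**Conclusion.** The point holds in limited form. Followed as written, the Protocol's rule can make elapsed time at T3 depend on arm, pacing and attendance, and it leaves some randomised families without a date. The spread does not require dropout: full attenders with no start lag run from 8.4 weeks before TAU (weekly) to 0.6 weeks after it (fortnightly). Larger gaps, 13.4 to 17.4 weeks for families leaving after sessions 1 to 3, depend on reading the last session as the last attended and on no start lag.

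The effect on the T3 estimates cannot be sized, because the documents give neither the distribution of finishing dates nor the rate of change of outcomes over time. T3 outcomes are secondary, so the T3 anchor does not touch the primary analysis. The T2 conflict does concern the primary time point. There the SAP model already states a common rule, and the remaining task is to align the other wording with it. This should be corrected.

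**What to change.** Reconcile the Protocol's Evaluation Design and Longitudinal follow-ups sections with the SAP's Design overview and model definitions, as follows:

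- **T2 assessment:** 16 weeks after minimisation in both arms, as the SAP model already states.
- **T3 assessment:** one fixed time from minimisation in both arms, for example the 7 months already used for TAU.
- **Windows and chasing:** the same in both arms, whatever the attendance, including families who stop early or never start.
- **Reporting:** T1 to T3 intervals by arm alongside the planned T1 to T2 summary. Treat any split by weeks as descriptive only.
- **Families already followed up:** state which timing rule applied to them.

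This concerns assessment dates only and leaves session scheduling as it is. The direct cost is wording and reminder dates.

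There are two real downsides. Families whose therapy overruns 16 weeks will complete T2 before their last session. Ten fortnightly sessions end at about week 18 with no lag, so this need not be rare. With T3 at 7 months, such a family would be measured 30.4 − 18 = 12.4 weeks after finishing, slightly under three months. Second, pilot baseline collection began in March 2023 and SAP version 1.1 is dated January 2025, so T3 timing may differ between families followed before and after the change. Those families are to be combined in one analysis, hence the need to record the rule applied to each.

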Appendix A: Progress Criteria

Project Implementation

Area	Question	Assessment method	Progression criteria	Red Amber Green
1. Fidelity	Are therapy sessions being recorded?	Calculate percentage of therapy sessions delivered that are recorded.	% therapy sessions recorded	≥75%
				74-50%
				<50%
2. Eligibility/ Referral	Do enough referrals received meet the eligibility criteria?	Calculate the percentage of referrals received during months 9-16 ^a of the pilot that were eligible to take part in the study.	% referrals received that met the eligibility criteria	≥75%
				74-50%
				<50%
3. Dosage	Do MBT-PP clients attend enough therapy sessions?	Calculate percentage of clients who attended under six and over six MBT-PP sessions.	i) % clients who were discharged having attended less than six sessions of MBT-PP	≤25%
				26-50%
				>50%

			ii) % clients who were discharged having attended six or more sessions of MBT-PP	
≥75%
 
74-50%
 
<50%

4. Practitioner training	Have MBT-PP therapists received enough training?	Report amount of the five days post-qualification training on MBT-PP received by therapists.	Number of days' training in MBT-PP received by therapists	
All therapists have received full 5 days of training in MBT-PP prior to delivering MBT-PP.
 
One or more therapists have received only 3 or 4 days of training in MBT-PP prior to delivering MBT-PP.
 
One or more therapists have received less than 3 days of training in MBT-PP prior to delivering MBT-PP.

5. Supervision	Do MBT-PP therapists receive enough supervision?	Calculate mean hours of supervision per month for MBT-PP therapists.	Mean hours of supervision per month per MBT-PP therapist (pro-rata if part-time).	
All therapists delivering MBT-PP receive 1.5 hours per month
 
One or more therapists delivering MBT-PP receive less than 1.5 hours, but more than 59 minutes per month
 
One or more therapists delivering MBT-PP receive less than 1 hour per month.

6. Practitioner capacity	Do MBT-PP therapists have the capacity to work with clients as intended?	Calculate percentage of families (or individual parents, if parents are attending therapy separately) that are contacted by the therapist within 2 weeks of being allocated to a therapist.	% families contacted by a therapist within 2 weeks of being allocated a therapist	
≥75%
 
74-50%
 
<50%

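### The 3-month follow-up (T3) is timed from the last MBT-PP session in one arm and from baseline in TAU, so its timing differs by arm and attendance, and the rule gives no date for families with no session

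*Protocol*

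**What the plan says.** **The rule for T3.** Protocol, Longitudinal follow-ups: "This will take place 3 months from the last session of MBT-PP, or, for those in TAU, 7 months". The TAU clause in full reads "for those in TAU, 7 months (the length of MBT-PP + 3 months) after the baseline measures".

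**Other statements about T2 and T3.**
- Protocol, Evaluation Design: "After 16 weeks (when MBT-PP is complete) the baseline measures will be repeated (post-intervention", and then "Three months after the end of the intervention (3-month follow-up), measures will be repeated a final time".
- Protocol, Participants: referrers are told that the last questionnaires come three months after parents finish.
- SAP, Design overview: T2 follows completion of treatment, then "Follow up assessments are completed 3 months later". No arm-specific rule is given.
- SAP, Primary outcome analysis (equation 2.0, Table 5) and Secondary outcome analysis: T2 is 16 weeks after minimisation in both arms.

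**Course length and attendance.** Protocol, Intervention: "The intervention consists of 10 sessions delivered over (approximately) 16 weeks" and "Sessions are usually delivered weekly or fortnightly, allowing participants some scheduling flexibility". Appendix A, criterion 3 tracks "clients who were discharged having attended less than six sessions of MBT-PP" and rates up to 25% as green.

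**Who is analysed.** The SAP's Analysis section analyses families as allocated whether or not parents take part. The Protocol's Intervention delivery section keeps families found unsuitable at the clinical assessment in the intention-to-treat (ITT) set.

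**How T3 is used.** SAP Table 4 and Longitudinal follow-up analyses give 18 T3 outcomes, all secondary, to be analysed as the primary outcome is. The elapsed-time check in Further analyses (equation 5.0) is written for the interval from baseline (T1) to T2.

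**The concern.** In a randomised comparison the assessment date should not depend on what happened after allocation. Under the Longitudinal follow-ups rule it does so in one arm only. The MBT-PP date moves with the last session attended, while the TAU date is fixed from baseline. A difference at T3 would then mix the effect of allocation with a difference in elapsed time, and within MBT-PP elapsed time would track attendance.

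Three further consequences follow:
- An MBT-PP family with no session has no last session to count from, so this rule sets no T3 date for a family that ITT retains.
- If T2 is fixed at 16 weeks, a family that stops very early could be due for T3 at or before T2.
- The SAP (Testing the theory of change mechanisms) may re-test the structural equation models with mediators at T2 and child outcomes at T3, to support a causal ordering. That ordering is lost for any family whose T3 does not come after its T2.

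The SAP accepts the principle for T2: it says that an interaction between arm and elapsed time would call the ITT estimate into question. It does not clearly carry that check to T3.

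**Working it through.** **Inputs.** From the Protocol: MBT-PP T3 is 3 months after the last session; TAU T3 is 7 months after baseline; the nominal course is 16 weeks; T2 is at 16 weeks. Assumptions: calendar months, and minimisation at about the time of baseline.

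**Conversion.** 1 month = 365.25 / 12 / 7 = 4.348 weeks, so 3 months = 13.04 weeks and 7 months = 30.44 weeks.

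**The plan's own figure.** 16 weeks = 16 / 4.348 = 3.68 months, and 3.68 + 3 = 6.68 months. The stated 7 follows if 16 weeks is counted as 4 months. It is a rounding, not an error.

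**T3 by week of last session.** MBT-PP T3 = week of last session + 13.04. TAU T3 = 30.44 for everyone. The last column takes T2 as fixed at week 16.

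| Last session (week) | MBT-PP T3 (week) | Relative to TAU T3 (weeks) | Relative to T2 (weeks) |
|---|---|---|---|
| 1 | 14.0 | -16.4 | -2.0 |
| 3 | 16.0 | -14.4 | 0.0 |
| 6 | 19.0 | -11.4 | +3.0 |
| 10 | 23.0 | -7.4 | +7.0 |
| 16 | 29.0 | -1.4 | +13.0 |
| 20 | 33.0 | +2.6 | +17.0 |
| none | no date | not defined | not defined |

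- The arms coincide only when the last session is at week 30.44 - 13.04 = 17.4.
- T3 meets T2 when the last session is at week 16 - 13.04 = 2.96.
- Full attenders vary too. Ten sessions from week 0 end at week 9 if weekly (T3 at week 22.0) and at week 18 if fortnightly (T3 at week 31.0). The week-0 start is illustrative.

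**The competing anchors side by side.**
- *Longitudinal follow-ups:* last session in MBT-PP, baseline in TAU. No date for a family with no session.
- *SAP Design overview, with T2 at the end of treatment:* T3 is always three months after T2, so they cannot coincide, but T2 now moves with attendance.
- *SAP Design overview, with T2 at 16 weeks as in equation 2.0:* T3 = 16 + 13.04 = 29.0 weeks for every family in both arms, including those with no session.
- *Protocol, Evaluation Design:* treats week 16 and the end of MBT-PP as the same moment, so it does not settle the matter for families that end at another time.

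Neither document says which statement governs.

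**The case against.** The strongest defence is that timing follow-up from the end of treatment is a recognised choice, and that the 7 months in TAU were plainly meant to match it. For a family that finishes at week 16 the arms are only 1.4 weeks apart. The SAP is dated later than the Protocol, and one reading of it (T2 at 16 weeks, T3 three months later) dates every family. All of this is fair. It narrows the point to a rule that works for a standard course and fails away from it. It does not remove the point, because the SAP does not say that it replaces the Protocol rule.

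Four stronger readings are tempting, and the documents do not support them:
- *Poor attenders are seen before effects have had time to develop.* The Protocol ties that time to the end of therapy, and its rule gives every MBT-PP attender three months after its own last session. What varies is time since baseline.
- *T3 will coincide with T2.* That needs T2 fixed at 16 weeks and a last session at about week 3 or earlier.
- *ITT is broken at follow-up.* Families with no session are kept as allocated, and nothing says that they would not be sent T3 measures. What is missing is a stated date.
- *The T3 estimate is biased by a known amount.* The documents give neither a rate of change in the outcomes over time nor a distribution of last-session dates. Late finishers measured after TAU would partly offset early stoppers. The 25% in criterion 3 is a ceiling for a green rating, counted in clients, not a forecast for families.

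The SAP's statement that T3 outcomes receive the same analyses as the primary outcome might also be read as extending the elapsed-time check to T3. The text does not make that clear.

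**Conclusion.** The point holds as a defect in the definition of T3. Under the Longitudinal follow-ups rule, time from baseline to T3 differs by arm and, within MBT-PP, depends on a post-randomisation event. The gap is 1.4 weeks for a course ending at week 16. It reaches 11.4 weeks before TAU for a last session at week 6, and 2.6 weeks after TAU for one at week 20. Families with no session have no date under that rule. The overlap with T2 is conditional, as stated above.

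The scope is limited to the 18 T3 secondary outcomes (of 35 secondary outcomes in all) and the optional T3 structural equation re-tests. The primary outcome at T2 is not affected by this rule. The size of any bias cannot be computed from the documents. The conclusion rests on the wording of the rule and calendar arithmetic, with minimisation taken to be close to baseline.

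**What to change.** Reconcile the Protocol's Evaluation Design, Participants and Longitudinal follow-ups sections and the SAP's Design overview to one T3 date for every family in both arms. Count it from baseline or randomisation, use the 7 months already set for TAU, apply a common window, and state that it covers families with few or no sessions. At 30.4 weeks, T3 then falls 30.4 - 16 = 14.4 weeks after a T2 at week 16.

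Report the achieved T1-to-T3 interval by arm. For T3 data already collected under the present rule, report that interval and apply the SAP's elapsed-time check to T3 as a sensitivity analysis. Add the caveat that in MBT-PP the interval is itself a post-randomisation variable tied to attendance, so adjusting for it is not a full remedy.

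The cost is wording in both documents and a change to the reminder schedule; no therapy session moves. There are two downsides:
- Time since the last session will vary around three months in MBT-PP: for example, 30.4 - 10 = 20.4 weeks for a last session at week 10, and 30.4 - 20 = 10.4 weeks for one at week 20.
- T3 data already collected will follow the present schedule, so the pooled sample will contain both. The Protocol's timeline has baseline collection ending in December 2024, before SAP version 1.1 (17/01/25), so this share may be large.
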